8.5 Other Endpoints

Summary reports from the immunological and biodistribution endpoint data will be provided. Tables similar to those seen in the following sections may also be provided to supplement these reports.

8.5.1 Immunology

Table 5A: Detailed Listing of Immunologic Results by Cohort and Patient

Cohort	Patient ID	Immunological Report Date	Visit	ELISA Assay Results (RU)		Positive/ Negative ELISA Response	Western Blot Required	Positive/Negative Western Blot Result
				Baseline	Post-Admin			

8.5.2 Biodistribution Endpoint

Table 5B: Detailed Listing of PCR by Cohort, Patient and Specimen
 (result includes the actual quantitative result or one of ND (negative), NQ < LLOQ (not quantifiable, < lower level of quantitation), or a shaded box indicating that the result was not available.)

Cohort	Patient ID	Specimen	Screening	Day 0	Day 1	Week 1	Week 2	Week 4	Week 12	Week 24	Week 36	Week 48
		Plasma										
		Buffy coat										
		Urine										

9.0 PATIENT PROFILES

An overall summary will be provided for each patient so that safety may be evaluated by case. The following sections contain a list of proposed tables and plots summarizing data from TDU13600 and LTS13619 that are included in each patient profile.

9.1 Baseline Characteristics

DEMOGRAPHY												
Patient ID	Cohort	Date of birth	Age	Gender	Race	Ethnicity	Study Eye	Screening Date	Surgery Date	Termination Date	Mutation	
COMMENTS:												

OCULAR MEDICAL HISTORY		
Condition	Study Eye	Diagnosis Date
COMMENTS:		

MEDICAL HISTORY		
Disease/Disorder	Date of Diagnosis	Ongoing
COMMENTS:		

PRIMARY ENDPOINTS (ADVERSE EVENTS)											
AE Description		Start Date (Study Day)	End Date Ongoing	Outcome	Severity	AESI	SAE	Related to Surgery	Related to Investigation Medicinal Product	System Organ Class	Preferred Term
COMMENTS:											

STUDY EYE EXAMINATION (ABNORMALITIES)								
Visit	Macular Edema	Abnormal Optic Nerve	Retinal Detachment	Intraretinal Hemorrhage	Subretinal Hemorrhage	Subretinal Fibrosis	Other	Specify Other
COMMENTS:								

IMMUNOLOGY					
Visit	ELISA Assay Result-Baseline	ELISA Assay Result-Post Admin	Positive/Negative ELISA Response	Western Blot Required	Positive/Negative Western Blot Result

¹The SC1 BCVA is not presented in the table because the SC2 BCVA is an average of the SC1 and SC2 BCVA values.

OCT														
	Central Macular Thickness		Macular Volume		Evidence of Treatment Efficacy		Increase in Cystoid Macular Edema		Unfavorable Change in Subretinal Fluid		Reported AE			
Visit	Study	Fellow	Study	Fellow	Study	Fellow	Study	Fellow	Study	Fellow	Study	Fellow	Study	OCT Data
COMMENTS:														

PERIMETRY														
	Static (GATE) Perimetry			Kinetic (SKP) Perimetry										
	Volume of Full Field Hill of Vision (Decibel Steradians)	111 pt grid-Volume of Full Field Hill of Vision (Decibel Steradians)		Study	Fellow	Study	Fellow	Study	Fellow	Study	Fellow	Study	Fellow	VI4E Isopter Area (Squared Degrees)
Visit	Study	Fellow	Study	Fellow	Study	Fellow	Study	Fellow	Study	Fellow	Study	Fellow	Study	Fellow
COMMENTS:														

FULL-FIELD ERG RESPONSE														
	Light adapted 3.0 flicker ERG	Light adapted 3.0 ERG a-wave	Light adapted 3.0 ERG b-wave	Dark adapted 3.0 ERG a-wave	Dark adapted 3.0 ERG b-wave	Dark adapted 0.01 ERG b-wave								
Visit	Amp	Imp Time	Amp	Imp Time	Amp	Imp Time	Amp	Imp Time	Amp	Imp Time	Amp	Imp Time	Comments	
COMMENTS:														

MEAN PEAK AMPLITUDES AND LATENCIES AT BASELINE (mfERG)														
	Amplitude (nV/deg ²) - max+min Latency (ms)													
	Ring 1		Ring 2		Ring 3		Ring 4		Ring 5		Ring 6		Comments	
Visit	Study	Fellow	Study	Fellow	Study	Fellow	Study	Fellow	Study	Fellow	Study	Fellow	Study	Fellow

[figure not shown]
MEAN PEAK AMPLITUDES AND LATENCIES AT BASELINE (mfERG)															
	Amplitude (nV/deg ²) - max+min Latency (ms)														
	Ring 1		Ring 2		Ring 3		Ring 4		Ring 5		Ring 6		Comments		
Visit	Study	Fellow	Study	Fellow	Study	Fellow	Study	Fellow	Study	Fellow	Study	Fellow	Study	Fellow	
COMMENTS:															

COMMENTS

[figure not shown]
SUMMARY CLINICAL OBSERVATIONS

OVERALL CONCLUSIONS

Visual Acuity

Intraocular Pressure (IOP)

ADMINISTRATION OF INVESTIGATIONAL PRODUCT					
Surgery Date	Full Dose Administered	Fluid-air Exchange Performed	Air Bubble Removed	Procedure Resulted in Retinal Tear	Complication(s) During Surgery
COMMENTS:					

PHYSICAL EXAM										
	Lymphatic/Hematologic		Musculoskeletal		Neurologic		Psychologic		Respiratory	
Visit	Abnormalities	Change from Baseline	Abnormalities	Change from Baseline	Abnormalities	Change from Baseline	Abnormalities	Change from Baseline	Abnormalities	Change from Baseline
COMMENTS:										

LENS ASSESSMENT									
		Natural Lens		Nuclear Score		Cortical Score		PCS Score	
Visit	Visit Date	Study	Fellow	Study	Fellow	Study	Fellow	Study	Fellow
COMMENTS:									

FUNDUS PHOTOS TDU Study													
	Treatment Efficacy		Increased Inflammation		Hemorrhage		Reported AE		Retinal Detachment		Comments		
Visit	Study	Fellow	Study	Fellow	Study	Fellow	Study	Fellow	Study	Fellow	Study	Fellow	
COMMENTS:													

NOTE: For Laboratory Listings, Yellow Indicates Outside of Site's Normal Laboratory Reference Range

²Neutrophil totals were not collected until September 2014

³ RDW-CV values were converted from RDW-SD values

KIDNEY AND LIVER FUNCTION												
	Kidney Function			Liver Function								
Visit	Creatinine (umol/L)	BUN (mmol/L)	Uric Acid (umol/L)	ALT (U/L)	AST (U/L)	Total Bilirubin (umol/L)	Alkaline Phosphatase (U/L)	Total Protein (g/L)	Albumin (g/L)	GGT (U/L)	Cholesterol (mmol/L)	
COMMENTS:												

Concomitant Medications									
Start Date	Action Date	Action	Medication Name	Indication	Route	Dose	Units	Schedule	Result of AE

Comments:

**SAR421869 TDU13600
COORDINATING CENTER**

August 30, 2019

[figure not shown]
Subject: **Table of Contents for Final Tables, Listings and Figures (TLFs) – SAR421869
Protocol TDU13600**

The purpose of this memorandum is to document that the Table of Contents for the final analysis for TDU13600 will differ from the Table of Contents in the currently approved version 2 of the SAP, dated 22JUL2016. The format of the tables will be the same as those in the SAP, except that the adverse event tables will be updated to the format used for the 23MAY2018 DSMB Report for SAR422459. The TOC and the adverse event table shells to be used for the final TLFs are included below.

Coordinating Center

Statistician Signature:

[figure not shown]
Date: 30AUG2019

Sponsor Statistician

Signature:

[figure not shown]
Date: 04SEP2019

Coordinating Center

Director Signature:

Date: 24SEP2019

TOC FOR ALL TLFs FOR TDU13600

- [Table 1A](#): Screening and Surgery Dates and Visit Completion by Cohort
- [Figure 1B](#): Patient Flow Diagram
- [Table 1C](#): Study Follow-up Completion and Withdrawal (including deaths)
- [Table 2A](#): Demographics Summary by Cohort
- [Listing 2B](#): Detailed Demographic Listing by Cohort
- [Listing 2C](#): General Medical History by Patient
- Listing 2D: Study Eye Ocular History by Patient
- Listing 2E: Fellow Eye Ocular History by Patient
- [Table 2F](#): Baseline Physical Examination Parameters by Cohort
- Table 2G: Reproductive Status by Patient
- Listing 2H: Detailed Surgery Listing by Patient
- Table 3A: Number and Percentage of Patients Experiencing TEAEs or No Events by Type of Event and Cohort
- Table 3B: Number of Patients Experiencing TEAEs by MedDRA SOC, HLGT, HLT, PT, and Cohort
- Table 3C: Number of Patients with TEAEs of Special Interest by MedDRA SOC, HLGT, HLT, PT, and Cohort
- Table 3D: Number of Patients with SAEs by MedDRA SOC, HLGT, HLT, PT, and Cohort
- Table 3E: Number of Patients Experiencing Inflammatory TEAEs by MedDRA SOC, HLGT, HLT, PT, and Cohort
- Table 3F: Number of Patients with TEAEs Related to IMP by MedDRA SOC, HLGT, HLT, PT, and Cohort
- Table 3G: Number of Patients with TEAEs Related to Procedure by MedDRA SOC, HLGT, HLT, PT, and Cohort
- [Table 3H](#): Listing of Adverse Events Prior to Treatment by Patient and Cohort
- [Table 3I](#): Listing of TEAEs by Patient and Cohort
- [Table 3J](#): Listing of Treatment Emergent Adverse Events of Special Interest by Patient and Cohort
- Table 3K: Listing of Treatment Emergent Serious Adverse Events by Patient and Cohort
- [Listing 3L](#): Ophthalmic Outcome Listing for Study Eye and Fellow Eye by Patient and Visit
- [Table 3M](#): Mean Changes from Pre-surgical BCVA by Cohort and Visit
- [Table 3N](#): Mean Changes from Pre-surgical IOP by Cohort and Visit

- Table 3O: Patients Experiencing BCVA Change in the Study Eye at Week 48 Following Treatment by Cohort
- Table 3P: Patients Experiencing Elevated IOP in the Study Eye at Week 48 Following Treatment by Cohort
- **Tables 3Q-3S:** Changes in Ophthalmic Inflammation in the Study Eye by Cohort and Visit
- Figures 3T-3V: BCVA in Study and Fellow Eyes by Patient in Cohort X
- Figures 3W-3Y: IOP in Study and Fellow Eyes by Patient in Cohort X
- Figure 3Z: Mean Changes in BCVA in the Study Eye over Time by Cohort
- Figure 3AA: Mean Changes in IOP in the Study Eye over Time by Cohort
- **Listing 3BB:** Listing of Patients with Abnormal and/or Clinically Significant Labs
- Listing CC: Abnormal Physical Examination Listing by Patient
- **Table 3DD:** Mean Change in Continuous Laboratory Parameters by Cohort and Visit
- **Listing 3EE:** OCT Listing by Patient and Visit
- Figures 3FF-3HH: Central Retinal Thickness (OCT) for Study and Fellow Eyes in Cohort X
- Figures 3II-3KK: Macular Volume (OCT) for Study and Fellow Eyes in Cohort X
- Table 3LL: Change from Baseline in Vital Signs by Cohort and Visit
- **Listing 4A:** Static (GATE) Perimetry Data by Patient
- Figures 4B-4D: Volume of Full Field Hill of Vision Measured by Static (GATE) Perimetry by Patient in Cohort X
- Figures 4E-4G: 111pt grid-Volume of Full Field Hill of Vision Measured by Static (GATE) Perimetry by Patient in Cohort X
- **Listing 4H:** Kinetic (SKP) Perimetry Data by Patient
- Figures 4I-4K: SKP Data in Study Eyes by Patient in Cohort X
- **Listing 4L:** Full Field ERG Response (Study Eye) Amplitude and Implicit Time Data by Cohort, Patient and Visit
- **Table 4M:** Mean Peak Amplitudes and Latencies at Baseline (mfERG) by Cohort and Patient
- **Table 4N:** Central Field (Rings 1-3) Summary mfERG Data by Cohort and Patient
- **Table 4O:** Peripheral Field (Rings 4-6) Summary mfERG Data by Cohort and Patient
- Listing 5A: Detailed Listing of Immunologic Results from Blood Samples by Cohort and Patient
- Listing 5B: Biodistribution Endpoint Data

ADVERSE EVENT TABLE SHELL FOR TDU13600

PRIMARY SYSTEM ORGAN CLASS HLGT: High Level Group Term HLT: High Level Term Preferred Term n(%)	Cohort 1 (1.4×10^5 TU) (N=3)	Cohort 2 (4.7×10^5 TU) (N=3)	Cohort 3 (1.4×10^6 TU) (N=3)	All Cohorts (N=9)
Any Class	X (X%)	X (X%)	X (X%)	X (X%)
SOC1	X (X%)	X (X%)	X (X%)	X (X%)
HLGT1	X (X%)	X (X%)	X (X%)	X (X%)
HLT1	X (X%)	X (X%)	X (X%)	X (X%)
PT1	X (X%)	X (X%)	X (X%)	X (X%)
SOC2	X (X%)	X (X%)	X (X%)	X (X%)
HLGT1	X (X%)	X (X%)	X (X%)	X (X%)
HLT1	X (X%)	X (X%)	X (X%)	X (X%)
PT1	X (X%)	X (X%)	X (X%)	X (X%)
HLT2	X (X%)	X (X%)	X (X%)	X (X%)
PT2	X (X%)	X (X%)	X (X%)	X (X%)
HLGT2	X (X%)	X (X%)	X (X%)	X (X%)
HLT3	X (X%)	X (X%)	X (X%)	X (X%)
PT3	X (X%)	X (X%)	X (X%)	X (X%)

Generated on DDMMYY HH:MM
By Path

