6.2 SECONDARY ENDPOINTS

The primary time points will be considered the 6- and 12-month visits.

To determine a delay in retinal degeneration following subretinal injection of SAR421869 through changes in function relative to the untreated contralateral eye utilizing the following retinal analytical techniques:

- Best-corrected visual acuity (BCVA).
- Contrast sensitivity.
- Indirect ophthalmoscopy.
- Visual function questionnaire VFQ-25/ CVAQC (when possible).
- Full dilated slit-lamp examination.
- Fundus photography – Panretinal photomontage.

- Visual field testing: Semi-automated Kinetic Perimetry (SKP) and Full-Field German Adaptive Thresholds Estimation (GATE) Static Perimetry, and microperimetry.
- Autofluorescence.
- Electroretinogram (ERG).
- Optical coherence tomography (OCT).

Adverse Events

The number and severity of any adverse events associated with SAR421869 administration will be assessed at each time point.

Immunology Endpoint

Humoral antibody response to SAR421869 administration.

Clinical Laboratory Tests

Hematology, biochemistry, urinalysis and other laboratory data will be measured at various time points throughout the study. Values will be flagged as High or Low if outside the laboratory normal range. Out of range values will be assessed as clinically significant (CS) or not clinically significant (NCS) by the investigator. CS out of range values will be recorded as adverse events. Blood for immunology and blood for PCR will also be taken at multiple time points throughout the study, as will urine samples for biodistribution assessment.

Biodistribution Endpoint

SAR421869 distribution in blood and urine will be assessed by polymerase chain reaction (PCR).

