8.5 DOSE-LIMITING TOXICITIES

Dosing will stop if a dose-limiting toxicity is encountered in a dosing cohort. Events that constitute a dose-limiting toxicity will be defined in the DSMB charter. Dose-limiting toxicities will include:

- Severe or persistent ocular inflammation.
- Other significant ocular toxicity (eg, large retinal detachment, evidence of direct toxicity).
- Other systemic toxicities (eg, acute allergic reaction).
- Any safety issue that has been identified that adversely changes the benefit/risk balance to study participants.

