7.3.1 Adverse Events

AEs will be coded using MedDRA® (last version available at time of database lock). All reported events for all patients with cohort, event description, event date, resolution date, severity, outcome, relatedness, SAE indication, duration, High Level Term (HLT), System Organ Class (SOC), and Preferred Term (PT) will be listed. Specifically, AEs prior to treatment, treatment emergent adverse events (TEAEs), (i.e., started or increased in severity after the patient receives IMP, including abnormal lab results, ECG, etc.) and TEAEs of special interest will be listed separately. An overall summary table of TEAEs will also be provided that includes the number and percentage of TEAEs and patients with at least one TEAE in each dose cohort with:

- A fatal AE (death)
- At least one serious AE
- At least one severe AE
- At least one AE related to IMP
- At least one TEAE related to procedure
- Without any AEs

In addition, tables will present both the number and percentage of TEAEs and patients with TEAEs by SOC, HLT, PT, severity and cohort. Adverse events of special interest (AESI), detailed in the protocol, will be summarized by SOC, HLT, PT, severity and cohort. AESIs will be indicated, where appropriate in the patient profile listing of AEs. AEs related to the IMP and serious adverse events (SAEs) will be indicated in the AE listing and described in detail in the body of the report. Specific grouping will be done for events inflammatory in nature in the eye. Summary tables will be presented both with the inflammatory events grouped and without the events grouped. All events with the following preferred terms will be considered inflammatory in nature in the eye:

- Anterior chamber cell
- Anterior chamber inflammation
- Choroidal effusion
- Conjunctivitis
- Eye inflammation
- Eye discharge
- Keratitis

- Macular oedema
- Subretinal fluid
- Uveitis
- Vitreous floaters

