8.3 Primary Outcome Analyses

8.3.1 Adverse Events

Table 3A lists the total and percentage of patients (overall and by cohort) experiencing no TEAE, any severe or serious TEAEs, a TEAE resulting in death and any TEAE related to IMP or the procedure. **Tables 3B to 3I** will include the MedDRA version used for grading as a footnote. All of the AEs presented will be graded using the same MedDRA version. **Tables 3B and 3C** summarize TEAEs and patients with at least one TEAE by MedDRA SOC, HLT, PT, severity and cohort and **Table 3D** summarizes treatment emergent AESIs by MedDRA SOC, HLT, PT, severity and cohort.

Table 3A: Number and Percentage of TEAEs and Patients Experiencing TEAEs or No Events by Type of Event and Cohort

Type of Event	Patients						Events					
	All	Cohort 1	Cohort 2	Cohort 3	Cohort 4	Cohort 5	All	Cohort 1	Cohort 2	Cohort 3	Cohort 4	Cohort 5
Fatal	N (%)	N (%)	N (%)	N (%)	N (%)	N (%)	N (%)					
No Events	N (%)	N (%)	N (%)	N (%)	N (%)	N (%)	N (%)					
Related to IMP	N (%)	N (%)	N (%)	N (%)	N (%)	N (%)	N (%)					
Related to Procedure	N (%)	N (%)	N (%)	N (%)	N (%)	N (%)	N (%)					
Serious	N (%)	N (%)	N (%)	N (%)	N (%)	N (%)	N (%)					
Severe	N (%)	N (%)	N (%)	N (%)	N (%)	N (%)	N (%)					

Table 3B: Number of TEAEs by MedDRA SOC, HLT, PT, Severity and Cohort (Event-based Counts)

SYSTEM ORGAN CLASS	HIGH LEVEL TERM (HLT)	PREFERRED TERM (PT)	COHORT								All Cohorts	
			1		2		3		4			
			Mild	Mild	Moderate	Mild	Moderate	Severe	Mild	Moderate	Mild	
SOC1	HLT1	PT1										
		PT2										
SOC2	HLT1											
		PT1										
		PT2										
All												

**Table 3C: Number of Patients Experiencing TEAEs by MedDRA SOC, HLT, PT, Severity and Cohort
(Patient-based Counts)**

(Note that if more than one event in each category is reported for a single patient, the most recent event of maximum severity is counted.)

SYSTEM ORGAN CLASS (SOC)	HIGH LEVEL TERM (HLT)	PREFERRED TERM (PT)	COHORT								All Cohorts	
			1		2		3		4			
			Mild	Mild	Moderate	Mild	Moderate	Severe	Mild	Moderate	Mild	
SOC1	HLT1	PT1										
		PT2										
SOC2	HLT1											
		PT1										
		PT2										
All												

**Table 3D: Number of TEAEs of Special Interest by MedDRA SOC, HLT, PT, Severity and Cohort
(Event-based Counts)**

SYSTEM ORGAN CLASS (SOC)	HIGH LEVEL TERM (HLT)	PREFERRED TERM (PT)	COHORT									
			1		2		3		4		All Cohorts	
			Mild	Mild	Moderate	Mild	Moderate	Severe	Mild	Moderate	Mild	Moderate
SOC1	HLT1	PT1										
		PT2										
	HLT1											

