		PT1										
		PT2										
All\												

Tables 3E and 3F summarize TEAEs and patients with at least one TEAE by MedDRA SOC, HLT, PT, severity and cohort, with all inflammatory events grouped into a single PT.

**Table 3E: Number of TEAEs by MedDRA SOC, HLT, PT, Severity and Cohort with Inflammatory Events Grouped
(Event-based Counts)**

SYSTEM ORGAN CLASS (SOC)	HIGH LEVEL TERM (HLT)	PREFERRED TERM (PT)	COHORT									
			1		2		3		4		All Cohorts	
			Mild	Mild	Moderate	Mild	Moderate	Severe	Mild	Moderate	Mild	Moderate
SOC1	HLT1	PT1										
		PT2										

		COHORT										All Cohorts			
		1	2	3				4		All Cohorts					
		Mild	Mild	Moderate	Mild	Moderate	Severe		Mild	Moderate	Mild	Moderate	Severe		
SOC2	HLT1														
	PT1														
	PT2														
All															

Table 3F: Number of Patients Experiencing TEAEs by MedDRA SOC, HLT, PT, Severity and Cohort with Inflammatory Events Grouped (Patient-based Counts)

(Note that if more than one event in each category is reported for a single patient, the most recent event of maximum severity is counted.)

			COHORT										All Cohorts			
			1	2	3				4		All Cohorts					
			Mild	Mild	Moderate	Mild	Moderate	Severe		Mild	Moderate	Mild	Moderate	Severe		
SYSTEM ORGAN CLASS (SOC)	HIGH LEVEL TERM (HLT)	PREFERRED TERM (PT)														
SOC1	HLT1	PT1														
		PT2														
SOC2	HLT1															
	PT1															
	PT2															
All																

Tables 3G and 3H summarize patients with at least one TEAE related to IMP and procedure, respectively, by MedDRA SOC, HLT, PT, severity and cohort.

Table 3G: Number of TEAEs Related to IMP by MedDRA SOC, HLT, PT, Severity and Cohort (Patient-based Counts)

SYSTEM ORGAN CLASS	HIGH LEVEL TERM (HLT)	PREFERRED TERM (PT)	COHORT								All Cohorts	
			1		2		3		4			
			Mild	Mild	Mild	Moderate	Mild	Moderate	Severe	Mild	Moderate	Severe
SOC1	HLT1	PT1										
		PT2										
SOC2	HLT1											
		PT1										
		PT2										
All												

Table 3H: Number of TEAEs Related to Procedure by MedDRA SOC, HLT, PT, Severity and Cohort (Patient-based Counts)

SYSTEM ORGAN CLASS	HIGH LEVEL TERM (HLT)	PREFERRED TERM (PT)	COHORT								All Cohorts	
			1		2		3		4			
			Mild	Mild	Mild	Moderate	Mild	Moderate	Severe	Mild	Moderate	Severe
SOC1	HLT1	PT1										
		PT2										

COHORT												
SOC2	HLT1	1		2		3		4		All Cohorts		
		Mild	Mild	Moderate	Mild	Moderate	Severe	Mild	Moderate	Mild	Moderate	Severe
SOC2	HLT1											
	PT1											

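### The August 2019 memo's adverse event summary tables drop the severity split and event counts specified in SAP 7.3.1, so no final summary table shows inflammatory events by severity and cohort

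*SAP*

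**What the plan says.** SAP 7.3.1 commits the analysis to two kinds of count and a severity split: "tables will present both the number and percentage of TEAEs and patients with TEAEs by SOC, HLT, PT, severity and cohort". It asks for adverse events of special interest (AESIs) to be summarised by severity and cohort as well. The shells in SAP 8.3.1 follow this. Table 3A is an overall summary, with a block for patients and a block for events, of those "experiencing no TEAE, any severe or serious TEAEs, a TEAE resulting in death and any TEAE related to IMP or the procedure". Tables 3B to 3H all carry severity. Ocular inflammation has its own pair, 3E (events) and 3F (patients); the second is headed "Table 3F: Number of Patients Experiencing TEAEs by MedDRA SOC, HLT, PT, Severity and Cohort with Inflammatory Events Grouped (Patient-based Counts".

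The memorandum dated August 30, 2019 changes the format of the adverse event tables to one used in a monitoring-board report for another product. Its term-level tables are of the form "Table 3B: Number of Patients Experiencing TEAEs by MedDRA SOC, HLGT, HLT, PT, and Cohort", and its one new shell has a single n (%) column per cohort, for three cohorts of three patients.

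Protocol 13.4.1 asks for less than the SAP: patients by system organ class, high level term and preferred term, an overall row for patients with a severe event, and a grouping of inflammatory ocular events.

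**The concern.** The primary objective is the safety and tolerability of ascending doses. One of the four dose-limiting toxicities in Protocol 8.5 is "Severe or persistent ocular inflammation". The rationale for the current amendment reports two serious uveitis cases with this vector technology, one of them in this study. Intensity of inflammation by cohort is therefore a summary that a reader will look for.

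The inflammatory grouping in SAP 7.3.1 is broad: it puts conjunctivitis, eye discharge and vitreous floaters with uveitis. Without severity, the overall row of memo Table 3E merges very different events, and even its uveitis row does not separate mild from severe.

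The memo describes the change as one of format and does not say why a pre-specified breakdown of the primary safety endpoint goes. The study is open-label, and the protocol amendment signed in August 2018 already described the Cohort 3 dosing and the uveitis case. No motive is suggested, but a reduction in safety summaries made at that stage should come with a reason.

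**Working it through.** The plan gives no figure to reproduce. The check sets the two sets of tables side by side and then asks what the remaining summary tables can tell a reader. Table numbers differ between the two sets, so each is labelled by its source.

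**1. Correspondence of tables**

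| Content | SAP version 2 | Memo |
|---|---|---|
| Overall summary | 3A: patients and events | 3A: patients only |
| All TEAEs by term | 3B (events), 3C (patients), by severity | 3B: patients, no severity |
| AESIs by term | 3D (events), by severity | 3C: patients, no severity |
| Serious events by term | none | 3D: patients (new) |
| Inflammatory events | 3E (events), 3F (patients), by severity | 3E: patients, no severity |
| Related to product | 3G (patients), by severity | 3F: patients, no severity |
| Related to procedure | 3H (patients), by severity | 3G: patients, no severity |

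**2. Counts**

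- Severity in the title: SAP 3B to 3H, 7 of 8; memo, 0 of 7.
- Event counts: SAP 3A, 3B, 3D and 3E, 4 of 8; memo, 0 of 7.
- Memo term-level tables that lose a severity split: 3B, 3C, 3E, 3F and 3G, which is five. Memo 3D has no predecessor, so it loses nothing.

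**3. What memo Tables 3A and 3E leave undetermined**

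In a cohort of 3, let S be the patients with any severe TEAE (Table 3A, assuming that its severe row is kept, since the memo shows no new shell for it). Let I be the patients with any inflammatory TEAE (Table 3E). A patient counted in both may have had a severe non-inflammatory event and a mild inflammatory one, so from these two tables alone:

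0 ≤ patients with a severe inflammatory TEAE ≤ min(S, I)

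- S = 1, I = 1: 0 to 1 of 3.
- S = 2, I = 3: 0 to 2 of 3.
- S = 0 or I = 0: exactly 0.

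One patient with a mild uveitis and one with a severe uveitis each print in Table 3E as 1/3 = 33%. SAP Table 3F would give the count directly.

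**4. Where severity or grade survives**

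- Memo Tables 3I and 3J are listings of TEAEs and AESIs. The SAP shells for these listings (numbered 3J and 3K there) have columns for severity, preferred term and cohort. The memo supplies no new listing shell, so I assume that those columns stand.
- Memo Listing 3L and Tables 3Q to 3S show inflammation grades and their changes. These are the examination grades of Protocol Appendix A, not adverse event severity, which Protocol 11.3 defines by impairment of function.
- Memo Table 3C counts AESIs. These include severe intraocular inflammation, but an ocular event can also qualify through loss of acuity or need for intervention (Protocol 11.5).
- Memo Table 3D counts serious events, and seriousness is not severity.

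No memo summary table crosses adverse event severity with inflammatory events by cohort.

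**The case against.** The strongest reply is that little is lost. The shell covers nine patients, every event is listed with its severity, and patient profiles (SAP 9) carry severity too. SAP 7.3.1 still has product-related and serious events described in detail in the report. Grade changes by cohort and visit remain, and the memo adds a serious-event table and listing that SAP version 2 lacked. The change is documented and signed by the statisticians. Much of this stands: a reader can find each severe inflammatory event, and event counts add little in cohorts of three. It does not replace a summary that the SAP specified, nor explain its removal.

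Stronger readings are tempting, and the documents do not support them:

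- **That the protocol promises these tables.** Protocol 6.2 says "The number and severity of any adverse events associated with SAR421869 administration will be assessed at each time point", but that is a general statement and sets no table layout. Protocol 13.4.1 is met by the memo's patient counts if Table 3A keeps its severe row.
- **That the final outputs cannot show severe inflammation.** This is true of the adverse event summary tables only; the listings and grade tables show severity or grade.
- **That all six term-level tables lose severity.** The serious-event table is new, so the number is five.
- **That dose-limiting toxicity is defined by adverse event severity.** The wording is severe or persistent, and Protocol 8.5 leaves the defining events to the monitoring board's charter.

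**Conclusion.** The point holds as a departure from the SAP. The memo's Tables 3A to 3G omit the severity split and event counts that SAP 7.3.1 and the SAP version 2 shells specify, state no reason, and leave 7.3.1 unrevised. Five term-level tables are affected. The consequence is modest but real: patients with severe inflammatory TEAEs per cohort can only be bounded from memo Tables 3A and 3E, and the exact number must be counted from the listings. This is a defect of summary reporting; it does not mean that data are lost or that the protocol is breached. It should be corrected because it concerns the primary safety endpoint of a tolerability trial that has already had a serious uveitis case.

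The conclusion assumes that the memo's Table 3A keeps its severe row and that the listings keep their SAP columns. One limit remains: a restored split would show severity by cohort, not by measured dose. The shell gives Cohort 3 a single dose of 1.4×10^6 TU, whereas the protocol's dosing table reports measured doses of 0.33×10^6 TU for one Cohort 3a patient and 2.4×10^6 TU for two.

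**What to change.** - **Minimum:** add maximum severity per patient (mild, moderate, severe) by cohort to memo Table 3E, or restore SAP Tables 3E and 3F under new numbers. The SAP's patient-based shells already count a patient once, at maximum severity, so no new rule is needed.
- **Preferably:** make the same addition to memo Tables 3B, 3C, 3F and 3G.
- **Optional:** event counts, since every event is listed.
- **In any case:** confirm that Table 3A keeps its severe row and that the listings keep their severity column. Describe any remaining departure from SAP 7.3.1, with its reason, in the study report, where SAP 1.0 places deviations from the plan.

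The cost is table programming for nine patients. Severity is already recorded for each event under Protocol 11.3, and the shells exist in SAP version 2.
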